This is a multicenter, randomized, clinical trial that will involve a minimum of 480 opiate abusers seeking opiate maintenance treatment. The study will be conducted at 10-12 sites with a maximum of 60 patients enrolled per site. Patients will be recruited at a rate of about 2 per week at each study site. Patient recruitment will last 30 weeks. Patients will remain on study medication for 16 weeks. After eligibility screening and signing a written informed consent, patients will be randomly assigned to one of four treatment groups: buprenorphine 1, 4, 8, or 16 mg/day. About 120 patients will be assigned to each group. Each site will enroll 15 patients into each group.

Patients will be administered their buprenorphine dose daily. No takeout dosages of medication will be allowed. Study sites will dispense buprenorphine 7 days per week.

After patients complete the 16-week protocol, they may be continued on the study drug under a new protocol or offered other treatment available at clinic. Patients who wish to be tapered from buprenorphine will be administered the induction schedule in reverse. If resources are available at the site, eligible patients can be switched to methadone or other treatments available after they are tapered from the buprenorphine. Otherwise, they will be tapered off the drug.

Inclusion Criteria

- 1. DSM-III-R diagnosis of current *opiate dependence* with daily use for past month.
- 2. Male and non-pregnant, non-nursing female, ages 18 or older.
- 3. Mentally competent to give informed consent.
- 4. Agreeable to being in protocol (signs informed consent).
- 5. Permanent residence within commuting distance of clinic.
- 6. Urine negative for methadone.

Exclusion Criteria

- 1. Acute hepatitis or any other acute medical condition that would make participation in the study medically hazardous for the patient, e.g., active tuberculosis, unstable cardiovascular or liver disease, unstable diabetes, or AIDS (not HIV-positive alone). Patients with elevated liver enzymes (SGOT or SGPT greater than 5 times the upper limit of normal) require more frequent clinical and laboratory monitoring than those specified in the schedule of data collection. Those with liver enzymes exceeding 8 times the upper limit of normal require at least weekly clinical and laboratory examinations and consultation from a specialist in liver disease before enrollment.
- 2. DSM-III-R diagnosis of current alcohol dependence or sedative-hypnotics dependence.

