The reduced data, i.e., 16 data points as explained earlier, one for each week will be used for this analysis. Since, treatment assignment will be the only covariate used, 16 regression coefficients will be estimated. A common regression coefficient estimated as $\hat{a}=\hat{o}c_i\hat{a}_i$ where \hat{a}_i is the regression coefficient for failure i (i=1, ..., 16) will be tested for statistical significance and the common hazard ratio $HR=e^{\hat{a}}$ will be estimated.

The estimate of common \hat{a} (common HR), if found to be statistically significantly different from zero (one) for the data pooled for all study centers for buprenorphine 8 mg versus buprenorphine 1 mg analysis only at \hat{a} =.05, will be indicative of the superiority of one drug over the other for FDA approval purposes.

This model was successfully used to analyze the ARC 090 study using a 17 dimensional model using the same data reduction algorithm as proposed for this study and buprenorphine was found to be statistically significantly better than both methadone 20 mg (p=.015) and methadone 60 mg (p=.037). The common hazard ratio was found to be .746 for the buprenorphine/60 mg methadone comparison and .706 for the buprenorphine/20 mg methadone comparison.

The common hazard ratio estimable from this model has an easy clinically understandable interpretation. For example, a common hazard ratio of .746 for the buprenorphine/60 mg methadone comparison means that the conditional probability of a buprenorphine treated addict, on the average, has a 25.4% less chance of abusing drug (opiate) compared to a methadone 60 mg treated addict provided none of them have yet used opiate. In other words, after the treatment begins, a buprenorphine treated addict has, on the average, 25.4% less chance of using opiate the first time compared to 60 mg methadone treated addict. In addition, the hazards ratios or comparative conditional probabilities for using the opiate the first time, the second time etc. are also estimable from \hat{a}_1 , \hat{a}_2 , etc. The relationship between the first, second positive urines etc. can also be studied by variance-covariance matrix of \hat{a} 's. Consequently, use of this model has the following advantages:

? This model can be used for censored data.

- ? Hazard ratios estimable from this model have easy clinically understandable interpretations.
- ? The relationship (pattern) between various positive urines can be studied.

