The time to first failures, second failures, etc., will be counted from the beginning of the study in days. For example, for the first positive week, if the first positive urine during study week seven was observed on day 45, the time to first failure will be 45 days. For the second positive week if the first positive urine during study week ten was observed on day 66, the time to second failure will be 66 days. If the week was considered positive because all samples during that week were missing, the time to first missing urine during that week will be the time to failure.

The **main** analysis for FDA approval purposes will be done by pooling data from all study centers and by computing â and HR. A subanalysis will be done for each study center to study treatment-center interaction. Subanalyses will also be done on the pooled data for males and females separately.

Common hazard ratios for 8 mg vs. 1 mg, 4 mg vs. 1 mg and 16 mg vs. 1 mg analysis will be plotted and displayed for comparison purposes only. Hazard ratios for each study week for each analysis will also be displayed.

Analysis Primarily for FDA Medical Review

For the analyses specified below, the following data reduction algorithm will be used:

- 1. If two or more urine samples for a given study week are found to be missing for a given patient, that week will be considered to be a missing week for that patient.
- 2. If at least two urine samples were available and analyzed for a given patient during a given week and if at least one urine sample was found to be positive for opiates, that week will be considered to be positive for opiates or a positive week. Otherwise, it will be considered to be a negative week.

The data for the missing weeks will be excluded from the following analyses:

1. Percent positive urines for each study week will be computed and plotted for each treatment group. For the data pooled for the total study period, a z statistic will be calculated and four preplanned *a priori* comparisons will be made between the proportions of positive urines for 1 mg vs. 4, 8 and 16 mg treatments respectively and for 1 mg vs. 4+8+16 mg comparison. Each of these *a priori* comparisons will be considered to be statistically significant at p value of .05 or below. Histograms will be plotted for percent positive urines for each of the four treatment groups for the total study period. No adjustment will be made for multiple comparisons.

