Percent positive urines will also be calculated for each urine testing opportunity and displayed.

- 2. The total number of positive urines for each patient will be rank ordered according to an algorithm specified by [name] and four preplanned a priori comparisons will be made between the number of positive urines for 1 mg vs. 4, 8 and 16 mg treatments respectively and for 1 mg vs. 4+8+16 mg comparison. Each of these a priori comparisons will be considered to be statistically significant at p value of .05 or below. No adjustment will be made for multiple comparisons.
- 3. ROC curves will be drawn for percent positive urines for each study week for each of the four pairs of treatment groups viz., 1 mg vs. 4, 8 and 16 mg and for 1 mg vs. 4+8+16 mg. No statistical analysis will be performed.

Exploratory Analyses to Identify Subgroups

Subgroups classified by body size/weight, sex and any other quantifiable factor as agreed to by FDA and the sponsor that may affect the suitability of one dose over another will be identified. Percent positive urines for each of these subgroups will be determined to identify which dose may be best for them. Urine sample profiles for all patients will also be displayed to determine which subgroup does better on what dose.

Analysis of Dropout Rates

Cox's single failure proportional hazards model will be used to analyze these data. Treatment assignment, age, sex and study center will be covariates used in the model.

The estimate of \hat{a} (hazard ratio) for treatment assignment adjusted for all other covariates, if found to be statistically significantly different from zero (one) for buprenorphine 8 mg versus buprenorphine 1 mg analysis only at \acute{a} =.05, will be indicative of the superiority of one drug over the other for FDA approval purposes.

Regression coefficients â and hazard ratios for 4 mg vs. 1 mg, 16 mg vs. 1 mg and 1 mg vs. 4+8+16 mg will also be estimated and plotted and displayed for comparison purposes only.

Analysis of Opiate Craving Scores and Global Rating Scores

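### The primary urine model ignores study center, and single-center fits are too small to show treatment-by-center interaction

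*Combined protocol and SAP*

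**What the plan says.** - **Primary model** (Analysis of the Incidence of Opiate Abuse): "Since, treatment assignment will be the only covariate used, 16 regression coefficients will be estimated". The main "analysis for FDA approval purposes will be done by pooling data from all study centers and by computing" the common coefficient and hazard ratio. No center term or stratum is mentioned.
- **Interaction** (same section): "A subanalysis will be done for each study center to study treatment-center interaction". No interaction term, heterogeneity test or criterion is given. Males and females are also to be analyzed separately.
- **Enrollment** (Method): "Each site will enroll 15 patients into each group"; "About 120 patients will be assigned to each group"; "The study will be conducted at 10-12 sites with a maximum of 60 patients enrolled per site"; the trial is a "clinical trial that will involve a minimum of 480 opiate abusers seeking opiate maintenance treatment".
- **Retention model** (Analysis of Dropout Rates), which also bears on approval: "Treatment assignment, age, sex and study center will be covariates used in the model".
- **Warning** (Summary of Assumptions Made in Sample Size Calculations): unexpected variation across centers, compared with the single-center ARC 090 study, could leave the sample too small.

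**The concern.** Two approval-bearing Cox analyses treat center differently, and no reason is given. The one that leaves center out is the urine analysis, although the plan itself names center variation as a risk to the sample size. Leaving a prognostic factor out of a Cox model pulls the hazard ratio toward 1. If the arms are also balanced on that factor, the ordinary standard error is too large and the test is conservative. Power for 8 mg against 1 mg is at stake.

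The interaction step raises a separate problem. Repeating the main model within each center asks for 16 coefficients and their covariance matrix from a few dozen patients. Differences between such results would mostly be noise, yet they could be read as real differences between centers.

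**Working it through.** **1. The plan's own power.** Noncentral F with 1 and 238 degrees of freedom, λ = 240·f², alpha .05. At f² = .02, λ = 4.8 and power is .588 (plan: 60%). At f² = .033, λ = 7.92 and power is .800 (plan: 80%). The figures reproduce, but the calculation has no center component.

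**2. Patients per center, 8 mg and 1 mg together.** At 15 per group: 2 × 15 = 30. At the 480 minimum there are 120 per group; over 10 sites that is 12 per group (24 patients), and over 12 sites 10 per group (20 patients).

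**3. Precision within one center.** ARC 090 gave a common coefficient of .348 in size, p = .015, with 53 + 55 = 108 patients. So z = 2.432 and SE = .348/2.432 = .143. Scale by SE(n) = .143·√(108/n), which assumes a similar event and dropout pattern. Power = Φ(.348/SE − 1.96) + Φ(−.348/SE − 1.96). The chance that an estimate falls on the wrong side of 1 is Φ(−.348/SE).

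| Patients | SE | Power | 95% CI around HR .706 | Wrong side of 1 |
|---|---|---|---|---|
| 30 | .271 | 25% | .41–1.20 | 10.0% |
| 24 | .303 | 21% | .39–1.28 | 12.6% |
| 20 | .332 | 18% | .37–1.35 | 14.8% |

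With the same true effect in every center, the chance that at least one of K centers points the wrong way is 1 − (1 − p)^K: 57% (8 sites of 30), 72% (12 of 30), 74% (10 of 24), 85% (12 of 20).

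**4. Sixteen-failure fits in one center (simulated).** At 15 per arm with no true effect, at least one coefficient could not be estimated in 76% of fits in simulation A. In simulation B it was 87% at 60% dropout, 69% at 30% and 97% at 80%. The plan does not define the weights that combine the coefficients. With inverse-covariance weights a true null was rejected in 41% (A), 24% (B) and 21% (C) of fits at 15 per arm; B gave 39% at 12 and 52% at 10. With equal weights the rate was about 5–7%.

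**5. Primary test, pooled against stratified by center.** Simulation B: 12 sites × 10 per arm, 300 trials per setting. Its assumptions are not in the documents: weekly positive probability .6, patient log-hazard SD .8, 60% dropout treated as censored, inverse-covariance weights, conditional log hazard ratio −.5.

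| Center SD (log hazard) | Error, pooled → stratified | Mean coefficient | Power |
|---|---|---|---|
| 0 | .07 → .08 | −.35 → −.37 | .84 → .87 |
| .4 | .04 → .07 | −.34 → −.37 | .82 → .87 |
| .8 | .02 → .06 | −.29 → −.35 | .65 → .85 |

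The Monte Carlo SE of the error rates is about .013. Stratified power is flattered by a slightly small SE. Using the simulated SD of the estimate instead, power = Φ(mean/SD − 1.96):

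- SD 0: .368/.124 gives .84, a gain of 0 points.
- SD .4: .366/.124 gives .84, a gain of 2 points.
- SD .8: .351/.120 gives .83 against .65, a gain of about 19 points.

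Simulation A (8 sites × 15 per arm, weaker effect, 250–300 trials, SE corrected in the same way, center SD in logits): at SD .8 power rises from 40% to about 52% and the coefficient moves from −.178 to −.198. At SD 1.2 power rises from 32% to about 45%. Simulation C (12 sites × 10 per arm, 100 trials, uncorrected): about .29 to .50 at SD .8.

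For scale: around an assumed 60% weekly positive rate (logit .405), a logit SD of .4 means centers from about 41% to 77% (.405 ± 1.96 × .4), and a logit SD of .8 from about 24% to 88%.

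**The case against.** **The planned test is valid and its replacement may be slightly liberal.** This stands. A reader might infer that omitting center inflates the type I error. It does not: the pooled test's error falls as centers diverge, while the uncorrected stratified test runs at about .05 to .08. The smaller coefficient is also a legitimate marginal effect, so attenuation alone is not an error.

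**The power loss rests on an assumed variance.** This stands. With similar centers there is little to recover, and a center SD of .8 is large.

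**The single-center false-positive rate depends on the weights.** This stands. A reader might infer that the center analyses will produce false heterogeneity in a fifth to two fifths of null centers. The documents do not support that, because they leave the weights undefined and equal weights bring the rate near nominal. Imprecision and non-estimable coefficients remain.

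**The plan does not state per-center p values, a .05 rule or the dimension of the center fits.** Correct. A 16-coefficient fit is the natural reading of a subanalysis of the main model, not stated text. The approval decision rests on the pooled comparison, so center results could color interpretation but not change that decision.

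**Balance within site is an enrollment target.** Also correct. The Randomization section describes telephone assignment and states no stratification or blocking by site. The conservatism of the pooled test depends on that balance being achieved.

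**Full adjustment would overload the model.** This stands. With 12 sites, 11 center terms plus age, sex and treatment make 14 terms; times 16 failures that is 224 coefficients for about 240 patients. Treatment-by-center terms for every failure would add 11 × 16 = 176 and bring back the small-center problem.

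**Conclusion.** The concern holds as a matter of efficiency and interpretability, not of validity. Leaving center out costs nothing to a few points of power if the center SD is 0 to .4, and about 12 to 20 points if it is .8. These figures rest on the simulation assumptions above and on a between-center variance that the documents do not give.

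The interaction step is the firmer half, because its main figures come from the plan's own pilot result. A center of 20 to 30 patients has 18% to 25% power at the pilot effect and an interval that spans 1, and some centers are expected to point the wrong way by chance even under one common effect. Estimating all 16 coefficients in a center usually fails, whichever weights are chosen.

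**What to change.** 1. Stratify each failure-specific Cox model by study center in the primary analysis. To guard against the slightly liberal test, pool very small sites under a rule set in advance, use a small-sample variance correction, or use a within-center permutation test.
2. Replace the center-by-center 16-coefficient fits with one common treatment effect per center, one pooled heterogeneity test with a stated criterion, and a forest plot. State that this test is itself limited. If the SD of the log hazard ratio between centers is .348, a Cochran Q test has power of about .59 (12 sites of 20) to .76 (12 of 30); at SD .2 it has .21 to .31.
3. For sex, use one common treatment-by-sex term in the pooled model in place of separate fits.
4. Do not add treatment-by-center terms for each of the 16 failures. Age and sex adjustment is optional, since no gain was shown.

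The cost is plan wording before unblinding; center and sex are already needed for the retention model. The named 1990 program may or may not handle strata, which cannot be checked from the documents. The downside is the liberal error rate if the protection in item 1 is left out.

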Since each urine sample found to be positive for opiates can be considered to be a treatment failure, up to 51 failures were observable in the 17-week (maintenance) ARC 090 study and up to 48 failures will be observable in the proposed 16-week study. Consequently, the analyses of data from these trials constitute analysis of multiple failures. Many methods to analyze multiple failures have been proposed but the one based on Cox's proportional hazards model by Wei and others (1989) imposes the least restrictive structure on the data and was used to analyze ARC 090 data and is proposed to be used for the multicenter study.

Briefly, this model estimates a regression coefficient between log hazard rate (dependent variable) and the treatment assignment (independent variable) for each failure. Tests of hypotheses to draw inference for each regression coefficient are available. A test of hypothesis to draw inference for a common regression coefficient which is a linear combination of individual regression coefficient is also available. Since the primary interest of the proposed study would be to compare the overall efficacy of the two treatments, the sample size calculations were based on the ability to draw inference for the common regression coefficient.

Since the parameter estimation may be mathematically extremely difficult for a 51- or a 48-dimensional model, the data will be reduced to 16 dimensions by deriving the index of weekly failures described earlier.

In the ARC 090 study, the sample sizes were 53 and 55 for the 8 mg buprenorphine and 20 mg methadone groups, respectively. The estimate of common regression coefficient was found to be 0.348 (p=.015) indicating superiority of buprenorphine over 20 mg methadone treatment. The sample sizes of 120 for each treatment group in the proposed study are more than double of what they were for the ARC 090 study and should provide sufficient cushion against the unexpected. However, the formal sample size/power calculations were still performed using the sample size calculation methods for multiple regression and correlation analyses given in Cohen (1988) using

Table 9.3.2 in this book.

Using Table 9.3.2, the following powers values were obtained for various values of f

f^2	ë	Correlation r	Power
.02	4.8	.14	60%
.15	36.2	.36	99%
.35	84.4	.50	99%

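### The common hazard ratio combines the 1st to 16th positive weeks but is described as a lower chance of first opiate use; the test stands, the stated effect does not

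*Combined protocol and SAP*

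**What the plan says.** All of this is in Statistical Considerations of the combined protocol and SAP.

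- **Definition.** Under Analysis of the Incidence of Opiate Abuse, the common coefficient is a sum of terms c_i × β_i, where β_i "is the regression coefficient for failure i (i=1, ..., 16) will be tested for statistical significance". The Sample Size Consideration section says that a test for a common "regression coefficient which is a linear combination of individual regression coefficient is also available", and ties this coefficient to overall efficacy.
- **Decision rule.** Superiority of 8 mg over 1 mg is judged by whether the common coefficient differs from zero at the .05 level.
- **Worked example.** The model was applied to ARC 090 "using a 17 dimensional model using the same data reduction algorithm as proposed for this study". "The common hazard ratio was found to be .746 for the buprenorphine/60 mg methadone comparison and .706 for the buprenorphine/20 mg methadone comparison".
- **Interpretation.** The .746 is said to mean "25.4% less chance of abusing drug (opiate) compared to a methadone 60 mg treated addict provided none of them have yet used opiate". The next sentence restates this: "a buprenorphine treated addict has, on the average, 25.4% less chance of using opiate the first time compared to 60 mg methadone treated addict".
- **Failure-specific coefficients.** The same paragraph adds that the "comparative conditional probabilities for using the opiate the first time, the second time etc. are also estimable from" the individual coefficients β_1, β_2 and so on.

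Easy clinical interpretation is then listed as one of three advantages of the model.

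**The concern.** The same paragraph gives the first-use meaning to two different quantities: the common hazard ratio e^β and the first-failure hazard ratio e^β_1. Conditioning on no earlier use describes β_1 only. The common coefficient also carries the times to the 2nd, 3rd and up to the 16th positive week, and those patients have already had a positive week.

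The restatement has a second fault. The plan's sentence just before it, conditional on no use so far, is a fair lay account of a hazard. The restatement drops the condition and reads 1 − HR as a percent reduction in the chance of an event, which it is not when the event is common.

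This is the plan's own explanation of its main efficacy estimate. A report that followed it would attach a first-use claim of the wrong kind, and probably the wrong size, to the primary result.

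**Working it through.** **1. The plan's figures reproduce.** 1 − .746 = .254, the stated 25.4%. For methadone 20 mg, the Sample Size Consideration section gives a common coefficient of 0.348, and e^(−0.348) = .706, the stated hazard ratio. The arithmetic is right, and these are hazard ratios from the common coefficient.

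**2. Does the common hazard ratio fix the first-failure one?** With β = Σ c_i β_i and weights summing to one, e^β = e^β_1 only if β_1 equals the combined value. The documents give neither the c_i nor ARC 090's β_1. To show how open this is, suppose equal weights over 17 failures (an assumption that the plan does not state). The other 16 coefficients must then average (17 × ln .746 − β_1)/16:

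| First-failure HR | Average HR of the other 16 (log scale) |
|---|---|
| 1.00 | 0.732 |
| 0.85 | 0.740 |
| 0.60 | 0.756 |

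Each row gives a common hazard ratio of .746. No single corrected first-use figure exists.

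**3. How large might the gap be under minimum-variance weights?** The multiple-failure model was simulated with 16 weekly failures and inverse-variance weights. Positivity, frailty, dropout and effect size are all assumed. Rows A to E use 120 per arm, 60 replicates and frailty SD 1.5.

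| Scenario (1 mg vs 8 mg) | First-failure HR | Common HR | Gap |
|---|---|---|---|
| A. Weekly positivity .90 vs .75, dropout 80% vs 60% | 0.750 | 0.711 | 0.039 |
| B. .90 in both arms at week 1, 8 mg improving later, dropout 80% vs 60% | 0.977 | 0.932 | 0.045 |
| C. .70 vs .50, dropout 30% in both | 0.732 | 0.701 | 0.031 |
| D. .60, odds ratio 0.4 from week 2, dropout 70% | 0.83 | 0.78 | 0.05 |
| E. As D, effect from week 1 | 0.67 | 0.65 | 0.02 |
| F. 300 per arm, 80 replicates, effect from week 2, dropout 70% (other settings not given here; indicative only) | 0.88 | 0.82 | 0.06 |

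The first failure carried about 0.6 to 0.7 of the weight in A to C and about 0.8 in D and E, which is why the gap is modest. In every row the common hazard ratio is the more favourable. In B it would be read as a 6.8% reduction (1 − 0.932), against 2.3% (1 − 0.977) for the first failure.

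**4. Hazard against chance.** Suppose .746 were the first-failure hazard ratio, hazards were proportional, and a share F of comparators ever had a positive week. The treated share is 1 − (1 − F)^.746. F is assumed.

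| F | Treated share | Relative reduction |
|---|---|---|
| .70 | .593 | 15% |
| .80 | .699 | 13% |
| .90 | .821 | 9% |
| .95 | .893 | 6% |

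The documents do not give F, but several features point to a high value. Entry requires daily opiate use over the past month, one positive sample makes a week positive, a week with all samples missing also counts, and there are up to 16 weeks. This step does not depend on the weights.

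**5. What β_1 measures.** Because a week with all samples missing is a failure, timed from the first missing sample, even e^β_1 concerns the first positive week as defined, not purely first opiate use.

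**The case against.** The strongest reply is that nothing in the decision rests on this wording. The test, the superiority rule, the data and the sample size all use the common coefficient, whatever words describe it. The quoted sentence is an illustration from ARC 090 against methadone 60 mg, and no section prescribes it for the trial report. Under minimum-variance weights the first failure dominates, so the first-use reading is a modest approximation. Failure-specific hazard ratios are already estimable, and a display of hazard ratios by study week is planned. All of this stands, and it is why the point is minor.

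What does not stand is that the illustration is harmless. It is offered as what the common hazard ratio means, and interpretability is a stated reason for the model. Saying that the effect holds on average does not help, because the sentence is still about first use. No other section corrects it.

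A reader might also infer a very large distortion. With equal weights, scenario F gives a common hazard ratio of 0.54 against 0.88 for the first failure, that is, a 46% reduction against 12%. The documents do not support that inference. They leave c_i undefined, nothing indicates equal weights, and the late-starting effect is an assumption. ARC 090 is reported as showing fewer positive urines at every maintenance time point.

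**Conclusion.** The interpretation contradicts the definition within the same section and should be corrected. The common hazard ratio is an overall hazard ratio across the 1st to 16th positive weeks, and it is not a reduction in the chance of first use.

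Two sizes should be kept apart. The gap between common and first-failure hazard ratios is unknown from the documents; it was about 0.02 to 0.06 in simulations that assume minimum-variance weights. The step from hazard to chance is larger: 25.4% becomes 15% to 6% for an assumed ever-positive share of 70% to 95%, under proportional hazards.

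A reader might infer that the efficacy conclusion itself is unsound, or that the trial would report a first-use benefit that is absent. Neither follows. The 8 mg versus 1 mg test remains a test of the common coefficient, and a missing first-use effect is possible but not shown to be likely. The error lies in the meaning and size attached to the result.

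**What to change.** In Analysis of the Incidence of Opiate Abuse:

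- Delete the reading of .746 as 25.4% less chance of first opiate use.
- Replace it with wording such as: *The common coefficient is a weighted combination of the log hazard ratios for the times to the 1st to 16th positive week, where a week may count as positive because all its samples are missing. Its exponential is an overall hazard ratio, not a ratio of chances.* The combination is of log hazard ratios, so the text should not call the result an average of hazard ratios. Naming the weights c_i in the same place would let readers judge how much the first failure contributes.
- For any statement about first use, report e^β_1 for the first positive week together with the percent of patients ever positive in each arm.

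The cost is wording and one or two descriptive lines. Of these, only the percent ever positive is new. No data collection, test or sample size changes. The stated claim becomes less favourable.
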